7.5.3.1 Overall Survival

OS will be defined as the time from randomization to the date of death due to any cause + 1 day. Patients who are alive at the time of the analysis will be censored on the last known date that they were alive. In addition, the following censoring rules will apply:

Scenario	Date of Censoring
Patients with no post-baseline information	Censored on the date of randomization + 1 day
Patients who are lost to follow-up or who withdraw consent for further follow-up	Censored on the last known date that they were alive

Survival rate at 1-, 2-, 3- and 5-year will be estimated using the Kaplan-Meier method. Additional sensitivity analyses are provided in Section 7.8.

7.5.3.2 Time to Symptomatic Progression

Time to symptomatic progression will be defined as the time from randomization to documentation in the CRF of any of the following (whichever occurs earlier) + 1 day:

- Development of a skeletal-related event (SRE): pathologic fracture, spinal cord compression, or need for surgical intervention or radiation therapy to the bone.
- Pain progression or worsening of disease-related symptoms requiring initiation of a new systemic anti-cancer therapy.
- Development of clinically significant symptoms due to loco-regional tumor progression requiring surgical intervention or radiation therapy.

Adverse event, concomitant medication, or survival follow-up CRFs may also be the source of these findings.

Time to symptomatic progression for patients who do not experience any of the events described above will be censored on the date on which they were last known to be event-free.

7.5.3.3 Time to Initiation of Cytotoxic Chemotherapy

Time to initiation of cytotoxic chemotherapy will be defined as the time from randomization to documentation of a new cytotoxic chemotherapy being administered to the patient (e.g., survival follow-up CRF) + 1 day.

Time to initiation of cytotoxic chemotherapy for patients who do not start a cytotoxic chemotherapy will be censored on the date of last contact.

7.5.3.4 Progression-Free Survival

In order to capture loco-regional disease progression, a secondary endpoint of progressionfree survival (PFS) will be assessed and defined as the time from randomization to first

ARN-509-003			
Statistical Analysis	Plan v7.0	26 June	2017

Page 15 of 34

documentation of BICR-confirmed radiographic progressive disease or death due to any cause (whichever occurs first) + 1 day.

Progressive disease (PD) will be based on RECIST v1.1, and further defined as follows:

- For patients with at least one measurable lesion, PD will be defined as at least a 20% increase in the sum of diameters of target lesions taking as reference the smallest sum on study (this includes the baseline sum if that is the smallest on study). In addition to the relative increase of 20%, the sum must also demonstrate an absolute increase of at least 5 mm. Furthermore, the appearance of one or more new lesions is also considered progression.
- For patients with only non-measurable disease observed on CT or MRI scans, unequivocal progression (representative of overall disease status change) or the appearance of one or more new lesions will be considered progression. For new bone lesions detected on bone scans, a second imaging modality (e.g., CT or MRI) will be required to confirm progression.

Progression-free survival data for patients without loco-regional disease will be censored on the date of the last tumor assessment (or, if no tumor assessment was performed after the baseline visit, at the date of randomization + 1 day). Additional censoring rules will vary according to whether the analysis is performed for US or ex-US regulatory purposes, as shown below; both results will be provided in the clinical study report.

Scenario	US regulatory guidance	ex-US regulatory guidance
Data from patients who are lost to follow-up or whose disease progression or death occurs after 2 or more consecutively missing or unevaluable tumor assessments	Censored on the date of the last tumor assessment that the patient was known to be progression-free	Time of progression will be determined using the first date when there is documented evidence of progression or death (whichever occurs earlier) regardless of missed or unevaluable tumor assessments
Patients that receive new systemic anti-cancer therapy prior to documented disease progression or death	Censored on the date of the last tumor assessment prior to the start of the new systemic anti-cancer therapy	Time of progression will be determined using the first date when there is documented evidence of progression or death (whichever occurs earlier) regardless of change of therapy

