### 13.2.2.4 Progression-Free Survival

In order to capture loco-regional disease progression, a secondary endpoint of progression-free survival (PFS) will be assessed and defined as the time from randomization to first documentation of BICR-confirmed radiographic progressive disease or death due to any cause (whichever occurs first) + 1 day.

Progressive disease will be determined based on RECIST v1.1, and further defined as follows:

- For patients with at least one measurable lesion, disease progression will be defined as at least a 20% increase in the sum of diameters of target lesions taking as reference the smallest sum on study (this includes the baseline sum if that is the smallest on study). In addition to the relative increase of 20%, the sum must also demonstrate an absolute increase of at least 5 mm. Furthermore, the appearance of one or more new lesions is also considered progression.
- For patients with only non-measurable disease observed on CT or MRI scans, unequivocal progression (representative of overall disease status change) or the appearance of one or more new lesions will be considered progression. For new bone lesions detected on bone scans, a second imaging modality (e.g., CT or MRI) will be required to confirm progression.

Progression-free survival data for patients without loco-regional disease will be censored on the date of the last tumor assessment (or, if no tumor assessment was performed after the baseline visit, at the date of randomization + 1 day). Additional censoring rules will vary according to whether the analysis is performed for US or ex-US regulatory purposes, as shown below; both results will be provided in the clinical study report.

Scenario	US regulatory guidance	ex-US regulatory guidance
Data from patients who are lost to follow-up or whose disease progression or death occurs after 2 or more consecutively missing or unevaluable tumor assessments	Censored on the date of the last tumor assessment that the patient was known to be progression-free	Time of progression will be determined using the first date when there is documented evidence of progression or death (whichever occurs earlier) regardless of missed or unevaluable tumor assessments

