3. RANDOMIZATION

Upon verification of inclusion and exclusion criteria, eligible patients will be centrally randomized in a 2:1 ratio to either ARN-509 or placebo. The randomization will be stratified as follows:

- PSADT (≤ 6 months vs. > 6 months)
- Bone-sparing agent use: Yes vs. No
- Loco-regional disease: N0 vs. N1

In order to ensure accurate and consistent determination of PSADT, the Interactive Voice Recognition System (IVRS) will also provide PSADT calculations (using a linear regression model of the natural logarithm of PSA and time) based on PSA values entered by the sites prior to randomization.

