The primary efficacy analysis will be completed when approximately 372 MFS events have occurred. The primary analysis will compare the MFS distributions in the two treatment groups using a two-sided log-rank test, stratified by PSADT (≤ 6 months vs. > 6 months), the use of a bone-sparing agent (Yes vs. No), and the presence of loco-regional disease (N0 vs. N1) at the 0.05 significance level. The non-stratified log-rank test will be provided as a sensitivity analysis. Additional sensitivity analyses are provided in Section7.8

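### The base censoring sentence for PFS names the wrong patients and contradicts the PFS definition in the same section

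*SAP*

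**What the plan says.** Both documents define PFS as time from randomization to first "documentation of BICR-confirmed radiographic progressive disease or death due to any cause" (Protocol 13.2.2.4; SAP 7.5.3.4 has the same definition). Progression follows RECIST 1.1. For patients with measurable lesions, "the appearance of one or more new lesions is also considered progression", with no limit by site, and new lesions also count for patients with only non-measurable disease.

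The base censoring rule comes next, in the same words in both documents: "Progression-free survival data for patients without loco-regional disease will be censored on the date of the last tumor assessment". A table then covers special scenarios, introduced by: "Additional censoring rules will vary according to whether the analysis is performed for US or ex-US regulatory purposes". Its rows deal with loss to follow-up or an event after missed scans ("disease progression or death occurs after 2 or more consecutively missing or unevaluable tumor assessments") and with subsequent treatment ("Patients that receive new systemic anti-cancer therapy prior to documented disease progression or death").

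Elsewhere, loco-regional disease is a baseline classification. SAP section 3 and Protocol 5.1 list the stratification factor as "Loco-regional disease: N0 vs. N1", and the stratified log-rank test in SAP 7.5.2 uses it in the same sense.

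**The concern.** A base censoring rule should apply to patients who have not had the endpoint's event. This one selects patients by a different attribute, so the event set it implies is not the one the definition gives.

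PFS is a confirmatory gate. SAP 7.5.3 tests the secondary endpoints in the order TTM, PFS, symptomatic progression, OS, cytotoxic chemotherapy, and the interim analysis of symptomatic progression goes ahead only if PFS is significant. If the sentence were programmed literally, the PFS test would use the wrong events, and the three later claims depend on that test. If the sentence were instead reinterpreted once results were known, it would be open to question whether the event set had been prespecified.

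**Working it through.** The plan gives no figure to reproduce. The check compares the sentence with the definition, the scenario table and the parallel endpoints, and then counts the conflicts.

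**1. Two literal readings**

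- Reading 1: no loco-regional progression on study.
- Reading 2: N0 at baseline, the documents' own use of the term.

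**2. Patient types**

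Cross nodal status (N0, N1) with outcome (loco-regional progression only, distant metastasis only, death only, no event): 2 × 4 = 8 types. By the definition, 2 × 3 = 6 are events and 2 are not.

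| Type | Definition | Reading 1 | Reading 2 |
|---|---|---|---|
| N0, loco-regional progression only | event | event | **censored** |
| N0, distant metastasis only | event | **censored** | **censored** |
| N0, death only | event | **censored** | **censored** |
| N0, no event | censored | censored | censored |
| N1, loco-regional progression only | event | event | event |
| N1, distant metastasis only | event | **censored** | event |
| N1, death only | event | **censored** | event |
| N1, no event | censored | censored | **no base rule** |

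- Reading 1: 2 (distant only) + 2 (death only) = 4 of 6 defined events censored, with no gap.
- Reading 2: 3 of 6 defined events censored (all in N0), and 1 of the 2 non-event types has no base rule.

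Adding patients with both loco-regional and distant progression gives 2 more event types, 8 in all. Reading 1 keeps both, so 4 of 8 conflict. Reading 2 censors the N0 one, so 3 + 1 = 4 of 8 conflict and the gap remains. The fractions depend on how the types are drawn. The contradiction does not.

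**3. Does other text override the sentence?**

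The scenario table is expressly additional. It does not restate the base case, so the US and ex-US analyses both rest on the faulty sentence, and comparing them would not expose it. SAP 7.2 and 7.5 give no general censoring rule that would take its place.

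**4. What was intended?**

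The MFS sentence (SAP 7.5.2) censors patients with neither metastasis nor death. The TTM sentence (SAP 7.5.3.5) censors patients without metastasis. Each names the absence of its own event. Both rows of the PFS table treat progression or death as the event. By the same pattern, the PFS sentence should name patients with neither progression nor death.

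**5. Size of the effect**

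The counts above are of types and carry no frequencies. Lost events or power would require the N0/N1 split, the PFS event count, the PFS hazard ratio and the loco-regional share of events. The documents give none of these.

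**The case against.** The best counter-argument is that nobody would be misled. The definition, the new-lesion text, both table rows and the MFS and TTM sentences all point to the same rule. Reading 1 has to treat disease as meaning progression, and Reading 2 is implausible in a section whose stated purpose is to capture loco-regional progression. Harm requires someone to program one phrase against everything around it.

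Much of this stands. The intent can be recovered, and the intended analysis is unaffected. A literal error might also be noticed: every MFS event is a PFS event under the definition, both endpoints are analysed together at about 372 MFS events, and a PFS count below the MFS count would look wrong.

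That does not make the sentence right. A reader must override the written rule to reach the intended one, and the section's stated purpose, if anything, makes Reading 1 easier to adopt by mistake. Detection by chance is a weak safeguard. SAP 7.8 plans sensitivity analyses only for MFS and OS, and the unstratified PFS test in Protocol 13.2.2 would use the same censoring rule.

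Two further objections are fair. The type counts are unweighted and measure the contradiction, not lost information. A protocol change also costs more than the edit itself, as set out under the fix.

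**Conclusion.** The concern holds. The base PFS censoring sentence is wrong as written in both documents, on either literal reading, and no current text corrects it. Followed literally, it censors 4 of 6 defined event types on one reading. On the other it censors 3 of 6 and leaves event-free N1 patients without a base rule. No effect on power or type I error is claimed.

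This is a drafting slip with a recoverable intent, not a design flaw. MFS, TTM and the intended PFS analysis do not change. It should still be fixed, because it is an operative rule for a gating endpoint whose event set needs one written meaning. The conclusion rests only on the wording of the two documents; the counts also assume the eight types listed.

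**What to change.** In SAP 7.5.3.4 and Protocol 13.2.2.4, change only the words that name the censored group, so that the rule applies to *patients without BICR-confirmed radiographic progressive disease (loco-regional or distant) or death*. Leave the rest of the sentence, including the censoring date and the provision for patients with no post-baseline scan, as it is. In the table above, the revised rule gives 0 conflicts and 0 gaps. Make the change before PFS results are known, if that is still possible.

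The cost is one sentence in each document, with no new data and no change to sample size, alpha or the intended analysis. Protocol 15.2 generally requires prior written IRB/IEC approval for an amendment, although Protocol 15.3 exempts purely logistical or administrative changes. Protocol section 13 places detailed methodology in the SAP, so a proportionate route is to correct the SAP now and the protocol at its next amendment.

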7.5.3.5 Time to Metastasis

Time to Metastasis (TTM) will be defined as the time from randomization to first evidence of BICR-confirmed radiographically detectable bone or soft tissue distant metastasis + 1 day.

ARN-509-003 Statistical Analysis Plan v7.0 26 June 2017

Page 16 of 34

TTM data for patients without metastasis will be censored on the date of the last tumor assessment (or, if no tumor assessment was performed after the baseline visit, at the date of randomization + 1 day). Additional censoring rules will vary according to whether the analysis is performed for US or ex-US regulatory purposes, as shown below; both results will be provided in the clinical study report.

Scenario	US regulatory guidance	ex-US regulatory guidance
Data from patients who are lost to follow-up or whose disease progression (development of metastasis) occurs after 2 or more consecutively missing or unevaluable tumor assessments	Censored on the date of the last tumor assessment that the patient was known to be metastasis-free	Time of progression will be determined using the first date when there is documented evidence of progression regardless of missed or unevaluable tumor assessments
Patients that receive new systemic anti-cancer therapy prior to documented disease progression (development of metastasis)	Censored on the date of the last tumor assessment prior to the start of the new systemic anti-cancer therapy	Time of progression will be determined using the first date when there is documented evidence of progression regardless of change of therapy

7.6 SAFETY ANALYSES

7.6.1 Adverse Events

Patients will be assessed for adverse events at each monthly clinic visit while on the study. Adverse events (AEs) will be graded according to the NCI Common Terminology Criteria for Adverse Events (CTCAE) Version 4.0 and coded to preferred term and system organ class (SOC) using the most recent version of MedDRA.

All AEs reported during the AE reporting period (inclusive of the 28-day post last dose of study drug period) will be considered as treatment-emergent adverse events and will be summarized by treatment group as treated using all patients in the SAFETY population.

For each treatment group, adverse event incidence rates will be summarized with frequency and percentage by MedDRA SOC and preferred term, with all patients treated in that treatment group as the denominator, unless otherwise specified. In addition, AE incidence rates will also be summarized by severity and relationship to study drug. Treatment-related AEs are those judged by the Investigator to be at least possibly related to the blinded study drug. Patients with multiple occurrences of events will only be counted once at the maximum severity to study drug for each preferred team, SOC, and overall. Deaths that occur within 28 days after the last dose of study drug are defined as on-study deaths.

Summary tables of the following AEs will be provided:

ARN-509-003	
Statistical Analysis Plan v7.0 26 June 20	17

Page 17 of 34

- Overall summary of AEs: the number and percentage of patients who experienced any AE, any serious adverse event (SAE), any treatment-related AE, any treatment-related SAE, any discontinuations due to an AE, and any deaths
- All AEs by SOC and preferred term
- All AEs by SOC, preferred term, and toxicity grade
- All AEs by decreasing frequency of preferred term
- Grades 3 or 4 AEs by SOC, preferred term and toxicity grade
- Drug-related AEs by SOC and preferred term
- Drug-related AEs by SOC, preferred term, and toxicity grade
- Drug-related Grades 3 or 4 AEs by SOC, preferred term and toxicity grade
- AEs that led to study drug discontinuation by SOC and preferred term. Study drug discontinuation will be determined from the End of Treatment CRF (where reason for termination is "Adverse Event") and the specific AE will be determined from the AE CRF page (where action taken is "Withdrawn from Study")
- AEs that led to study drug discontinuation by SOC, preferred term, and toxicity grade.
- All SAEs by SOC and preferred term
- All SAEs by SOC, preferred term, and maximum severity
- Deaths will be summarized by time period (on-study vs. during follow-up) and cause of death.

Patient listings of all Grades 3 or 4 AEs, all SAEs, AEs that led to study drug discontinuation and all deaths will be provided as well.

Narratives will be written for the following patients in the final clinical study report:

- Patients who die within 28 days of the last dose of study drug
- Patients who discontinue study drug due to adverse events
- Patients who have a serious adverse event
- Patients who experience a seizure
- Grade 3 or higher adverse events of special interest

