Sixteen subjects participated in an evaluation of AR binding in vivo using  $^{16}\beta$ -[ $^{18}\text{F}$ ] fluor- $\alpha$ -dihydrotestosterone (FDHT) positron emission tomography (PET)/CT scan. Apalutamide treatment reduced FDHT uptake across all dose levels (30 to 390 mg dose levels). A plateau was reached at approximately 120 mg (with FDHT uptake near background) indicating saturation of AR binding. The mean plasma trough levels associated with this dose (2.5  $\mu\text{g/mL}$ ) were at the lower end of the range that produced tumor regression in the LNCaP/AR mouse model. Steady state plasma levels at the 240 mg dose level (3 to 6  $\mu\text{g/mL}$ ) were more in the range sufficient to elicit a tumor response in the mouse xenograft model. Therefore, the 240 mg daily regimen was chosen for Phase 2 and Phase 3 dosing.

Apalutamide was rapidly absorbed, with measurable plasma concentrations within 30 minutes after ingestion of a single oral dose of 1 to 16 soft gelatin capsules (total apalutamide dose, 30 to 480 mg). On average, peak plasma concentrations occurred 2 to 3 hours after administration in each dose group. The increases in plasma  $C_{\text{max}}$  values and in the area under the plasma concentration curve (AUC) were linear and dose proportional. Plasma apalutamide concentrations declined slowly, with a mean half-life value at steady-state of 4 days.

The percentage of patients with PSA reductions of  $\geq 50\%$  at 12 weeks were 91% for the Group 1, 88% for the Group 2, and 24% for Group 3. Similar data were observed after 24 weeks. The data available to date indicate that apalutamide shows durable PSA responses in NM-CRPC and early mCRPC (before treatment with abiraterone acetate or chemotherapy). Apalutamide also has activity in a subgroup of patients with mCRPC that have progressed on abiraterone acetate. For the NM-CRPC subgroup, the metastasis-free survival at 12 months was 87% and with a median follow-up of 15 months the time to PSA progression had not been reached.

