### **9.2.2 Non-Serious AE Reporting**

Adverse events should be recorded on the AE CRF from the time the patient has signed the informed consent at screening (see Section 8.2) until 28 days after the last dose of study drug. All events should be followed to their resolution, until the Investigator assesses them as stable, irreversible, or until the patient is lost to follow-up, whichever comes first. If a patient begins a new systemic anti-cancer therapy, the AE reporting period for non-SAEs ends at the time the new treatment is started.

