### 13.3.1 Analysis of Adverse Events

Adverse events (AEs) will be graded according to the NCI Common Terminology Criteria for Adverse Events (CTCAE) Version 4.0 and coded to preferred term and system organ class (SOC) using the most recent version of MedDRA.

All AEs reported from the first dose of study drug until 28 days after the last dose of study drug will be considered as treatment-emergent AEs and will be summarized by treatment arm.

For each treatment arm, adverse event incidence rates will be summarized with frequency and percentage by MedDRA SOC and preferred term, with all patients treated in that treatment arm as the denominator, unless otherwise specified. In addition, AE incidence rates will also be summarized by severity and relationship to study drug. Treatment-related AEs are those judged by the Investigator to be at least possibly related to the blinded study drug. Adverse events with missing severity or relationship to study drug will be classified as severe and treatment-related, respectively. Patients with multiple occurrences of events will only be counted once at the maximum severity to study drug for each preferred term, SOC, and overall. Deaths that occur within 28 days after the last dose of study drug are defined as on-study deaths.

Summary tables and individual patient listings will be prepared as per the Statistical Analysis Plan. An additional analysis by formulation subgroups will be performed as outlined in the Statistical Analysis Plan.

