2. STUDY DESIGN

This is a randomized (2:1), multicenter, double-blind, placebo-controlled, Phase III clinical trial evaluating the efficacy and safety of ARN-509 versus placebo in approximately 1200 men with high risk non-metastatic (M0) castration-resistant prostate cancer (NM-CRPC), defined as PSA Doubling Time (PSADT) \leq 10 months.

ARN-509 will be administered orally on a continuous daily dosing schedule, at a starting dose of 240 mg per day in the treatment group. Matched placebo will be administered orally on a continuous daily dosing schedule, at a starting dose of 240 mg per day in the placebo group.

Patients will be followed for safety and efficacy as per the schedule of assessments and will remain on study treatment until documented radiographic progression (development of distant metastases as assessed by blinded independent central review [BICR]) or the development of unacceptable toxicity.

Patients discontinuing treatment due to documented radiographic progression will enter the survival follow-up period, where they will be followed for the development of symptomatic progression, initiation of subsequent anti-cancer therapies (in particular, cytotoxic chemotherapy) every 4 months until death, loss of follow-up, or withdrawal of consent, whichever comes first.

Patients discontinuing treatment prior to documented radiographic progression will also enter the survival follow-up period where they will continue to have scheduled disease assessments every 4 months until documented radiographic progression, and will be followed for the development of symptomatic progression and initiation of subsequent anti-cancer therapies (in particular, cytotoxic chemotherapy) every 4 months until death, loss of follow-up, or withdrawal of consent, whichever comes first.

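### AEs are reported only as crude percentages while treatment runs to metastasis, so the arms may have unequal time at risk and percentages for AEs that accrue over time are not directly comparable

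*SAP*

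**What the plan says.** SAP 7.6.1 sets the summary measure: "adverse event incidence rates will be summarized with frequency and percentage by MedDRA SOC and preferred term". The denominator is everyone treated in that arm, except where another is named. The counting rule is "Patients with multiple occurrences of events will only be counted once at the maximum severity".

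The observation window follows dosing. The SAP counts as treatment-emergent "All AEs reported during the AE reporting period (inclusive of the 28-day post last dose of study drug period"). Protocol 13.3.1 has "All AEs reported from the first dose of study drug until 28 days after the last dose of study drug". Protocol 9.2.2 closes the window earlier for some patients: once new systemic anti-cancer therapy begins, "the AE reporting period for non-SAEs ends at the time the new treatment is started".

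Dosing follows the primary endpoint. By SAP section 2, patients "will remain on study treatment until documented radiographic progression", meaning distant metastasis on central review, or until unacceptable toxicity.

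Drug exposure is summarized by arm (SAP 7.4.3), and so are follow-up duration and reasons for discontinuation (SAP 7.3). None of these is linked to an AE table. SAP 7.6.1, the by-formulation safety tables (SAP 7.9.4), the AE table shell (SAP Appendix 2) and Protocol 13.3.1 contain no rate per patient-time, no time-to-first-AE analysis and no fixed-window analysis.

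**The concern.** A crude percentage answers how many treated patients had the event while under observation. It compares two arms fairly only if they are observed for similar lengths of time. Here the length of observation depends on metastasis, and the trial is designed to show that apalutamide delays metastasis. If it does, its patients are watched for AEs for longer. An event with the same underlying hazard in both arms will then appear in a larger share of apalutamide patients.

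The point matters most for events that build up over time. SAP Appendix 3 names five special-interest categories: seizure, skin rash, changes in thyroid function, fall and fracture. Falls and fractures can plausibly keep occurring for as long as men in this population are followed, with or without the drug. From percentages alone, a reader cannot tell how much of a difference is drug effect and how much is time at risk.

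**Working it through.** **Inputs from the documents.** MFS HR 0.70, two-sided alpha 0.05, 90% power, 372 events and placebo median MFS 25 months (SAP section 4). Allocation 2:1 (SAP section 3), 800 and 400 patients (Protocol synopsis). Accrual over 24 months with 75% in the second year (SAP section 4). Minimum follow-up 9 months, so cutoff at month 24 + 9 = 33, and projected study duration 65 months (Protocol synopsis).

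**Assumptions added here.** MFS is exponential. Accrual is uniform within each year. Treatment stops at an MFS event or at data cutoff. The 28-day tail is ignored. There is no other discontinuation unless stated.

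**Step 1: the plan's own figure.** Schoenfeld events at 2:1 are (1.960 + 1.282)² / [(2/9) × (ln 0.70)²] = 371.7, so 372. This matches. With the same inputs the exponential model projects about 385 MFS events at month 33, close enough to 372 to serve as a proxy for time on treatment.

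**Step 2: time on treatment.** The monthly hazards are λ = ln 2 / 25 = 0.0277 (placebo) and 0.70 × 0.0277 = 0.0194 (apalutamide). Mean time on treatment is the average over entry times of (1 − exp(−λf)) / λ, with f = cutoff − entry time.

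**Step 3: crude AE percentage with no drug effect.** For a constant AE hazard h, equal in both arms, the crude proportion is the average over entry times of [h / (h + λ)] × [1 − exp(−(h + λ)f)]. Setting placebo to 20% gives h = 0.0166 per month at month 33 and 0.0087 at month 65.

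| Cutoff, HR 0.70 | Months on treatment, placebo | Months on treatment, apalutamide | Ratio | AE on placebo | AE on apalutamide |
|---|---|---|---|---|---|
| Month 33 | 13.9 | 14.9 | 1.08 | 20% | 21.4% |
| Month 65, no crossover | 26.9 | 31.9 | 1.18 | 20% | 23.3% |

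A discontinuation hazard of 1% per month in both arms (an assumption) lowers the ratios only to 1.07 and 1.16.

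**Step 4: does the adjusted rate remove the gap?** At month 33, mean time to first AE, stopping or cutoff is 12.03 months (placebo) and 12.89 months (apalutamide). First-event rates are 0.200 / 12.03 × 1,200 and 0.2144 / 12.89 × 1,200. Both are about 20 per 100 patient-years, so the ratio is 1.00, as it should be.

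**Step 5: early-onset events.** If all AE hazard falls in the first 3 months (h = 0.05 per month), the proportions at HR 0.70 are 13.4% and 13.5%, a relative difference of about 1%.

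**Step 6: unequal stopping for toxicity.** The documents give no discontinuation rates for this trial. Protocol 1.1.3 reports that in the Phase II non-metastatic cohort 8 of 51 stopped for AEs and 7 of 51 for progression. From the same section's 87% MFS at 12 months, the event hazard is −ln(0.87) / 12 = 0.0116 per month. Scaling by 8/7 gives an assumed AE-stopping hazard of 0.0133 per month on apalutamide. Results at HR 0.70, month 33:

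| AE stopping on placebo (assumed) | Exposure ratio | AE on apalutamide if 20% on placebo |
|---|---|---|
| None | 0.96 | 19.2% |
| Half the apalutamide rate | 1.01 | 20.3% |
| Same as apalutamide | 1.07 | 21.3% |

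The gap closes when stopping on apalutamide exceeds that on placebo by 0.0277 − 0.0194 = 0.0083, or about 0.8% per month.

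**The case against.** **Direction.** A reader might infer that apalutamide's AE percentages will be inflated. The documents do not establish that. Step 6 shows that a stopping rate drawn from the sponsor's own Phase II cohort can remove or reverse the exposure gap at the planning HR. This objection stands, so the point has to be conditional. It does not remove the problem, because a rate per patient-time corrects unequal exposure in either direction.

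**Size.** A reader might also take the Phase II statement that "the metastasis-free survival at 12 months was 87" percent as evidence of a larger gap than planned. Put into the model without other stopping, it gives 16.1 months on apalutamide (+16%), and 20% becomes 22.9%. But it comes from 51 single-arm patients. A simple binomial 95% interval on 87% with n = 51 is about 78% to 96%, and the planning HR implies 79% at 12 months, which lies inside it. With the step 6 stopping rate on apalutamide and none on placebo, the ratio falls to 1.03. The figure cannot carry a claim of a larger gap.

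**Nature of the tables.** SAP 7.6.1 plans descriptive AE tables with no test. A crude percentage remains valid as the proportion of patients affected while on treatment. Exposure by arm is reported, so an imbalance would be visible, and nothing bars supplementary rates. All of this is fair, and it keeps the matter minor. Visible exposure still does not tell a reader how much of a particular AE difference it explains. The SAP allows another denominator where specified, but specifies none.

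**Replacing the percentages.** It is tempting to rest between-arm statements on patient-year rates alone. That goes too far. For an event concentrated in the first weeks, later person-time only dilutes the rate in the longer-exposed arm. With a true crude ratio of 2.0 and exposure ratios of 1.08 to 1.16, the rate ratio would be about 2.0 / 1.08 = 1.85 to 2.0 / 1.16 = 1.72, which understates harm.

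**Conclusion.** The concern holds in conditional form. Because AE collection is tied to dosing and dosing to metastasis, the two arms need not have equal time at risk, and the plan has no AE measure that accounts for it. Under the planning assumptions the effect is modest at the MFS analysis: about 8% more exposure and 1.4 percentage points on a 20% AE. By month 65 without crossover it is about 18% and 3.3 points. These sizes assume exponential MFS, a constant and equal AE hazard, and no other discontinuation. Early-onset AEs are hardly affected, and the sign of the gap depends on discontinuation rates that the documents do not give. The percentages are not wrong in themselves. They are insufficient for comparing arms on events that accrue over time. This is a worthwhile addition to the SAP and does not threaten the trial's conclusions.

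**What to change.** In SAP 7.6.1, add exposure-adjusted rates by arm beside the existing percentages: patients with a first event per 100 patient-years at risk. Define time at risk as the treatment-emergent window, ending at the first event if one occurs. Provide the rates for the overall AE summary and for the five special-interest categories in SAP Appendix 3. State that between-arm differences in events that accrue over time will be interpreted with both measures in view. For any cutoff after unblinding, say how time after crossover from placebo is counted.

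The cost is a few extra tables. The dosing dates are already used for treatment duration in SAP 7.4.3, so no new data are needed. The drawback is that a constant-rate summary is less informative for early-onset events. For those, the percentages should remain the main display.
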